Participants randomized to TAU will receive similar payments at the same time points as participants in the intervention arm-1 and arm-2 groups. At the completion of each of the follow-up sessions all participants are compensated for their time.

Proposed Analyses

Aim 1 is a 3-year RCT involving community and ED-enrolled Black / Latinx PWUO who will be screened and enrolled (N=252) **Primary outcomes** will be based on remote and/or in-person follow-up assessments at 3-, 6-, and 12-months and consists of self-reported linkage to primary care-based OUD services (i.e., time to initial receipt of buprenorphine in primary care). **Secondary outcomes** include durability of treatment effect at 52 weeks (e.g., continuous retention in OBOT with buprenorphine), receipt of social services, and longitudinal engagement with the proposed intervention (up to 26 weeks).

Our primary hypothesis is that the rate of linkage to OBOT, i.e., time to first buprenorphine prescription, will be highest among PWUO participants randomized to texting + PRC, followed by those randomized to texting only, then to TAU. To assess this hypothesis, we will utilize Cox proportional hazards (PH) regression to investigate differences in time to service linkage (in days) by intervention group. Cox PH regression is a method for investigating the effect of several variables on the time to a specified event¹⁷⁰. Cumulative hazards functions for the intervention groups will be examined using Nelson-Aalen plots and use the supremum test which uses martingale residuals to check the proportional hazards assumption. If the assumption is violated such that there is no difference in the direction of the association but there is variation in the magnitude of the association, i.e., the hazards ratio (HR) changes over time, then the coefficient that we estimate for that covariate is akin to an 'average effect' over timepoints that are observed in a dataset and the Cox PH model will perform moderately. If the hazards cross, i.e., a change in the direction of the association, the Cox PH model will perform poorly, and we will extend the Cox model to allow for nonproportional hazards using time dependent covariates. Intervention group as assigned will be the sole explanatory variable in the models (see **Methodological Considerations and Alternatives**).

Secondary and exploratory analysis will rely on data collected at 3-, 6-, and 12-month follow-up surveys that will permit analysis of secondary outcomes of: (1) durability of treatment effect at 52 weeks (e.g., continuous retention in OBOT with buprenorphine); (2) engagement with social services; and (3) longitudinal engagement with the proposed intervention (up to 26 weeks). For these analyses, we will use generalized linear mixed effects regression to model binary outcomes indicating longitudinal engagement in 26-week treatment (yes/no) and continuous retention in buprenorphine treatment at 3-, 6-, and 12-months (yes/no) with no more than a 28-day gap in receiving an active buprenorphine prescription over each period. These models will include a participant-specific random intercept to account for the repeated-measures structure of the data.

Methodological Considerations and Alternatives: To assess whether randomization was successful, we will compare the distribution of demographic characteristics, PhenX consensus measures, medical/psychiatric history, technology use patterns, and risk behavior variables (see *Data Collection*) by intervention arm. Variables contributing to baseline imbalance will need to be included as adjustment variables in regression models.

Missing Data and Sensitivity Analysis will rely on ensuring that the model assumption of non-informative study dropout or missing at random is reasonable and avoid potential bias, we will compare dropout rates between intervention groups as well as other measured variables, e.g., medical/psychiatric history, technology use patterns, and risk behavior variables. If there is empirical evidence of nonrandom dropout, we will model the dropout event using available factors to identify and estimate their influence. To meet missing at random model assumption, variables that predict dropout will be included as auxiliary variables via multiple imputation.

Intervention fidelity is an important consideration with "real world" research interventions. Lack of fidelity can increase the possibility of a type I or II error and make study findings difficult to interpret. Certain study design considerations are incorporated to support intervention fidelity, e.g., use of a standardized, established training for PRCs, collection of important study measures like PRC-participant communication logs. In the data analysis, we will confirm that the intervention is received in the same way within each intervention arm across participants and through time by comparing type and frequency of topics discussed as well as process measures (see Data Collection); we will also compare fidelity metrics by participant characteristics. In the unlikely event that we do not observe an intervention effect, participant data on social determinants, risk behaviors, patient-centered care, clinical and social services use, and technology use will be instrumental in the interpretation of study findings and recommendations for practice.

The **sample size**, N=252, was chosen to provide sufficient power for analyses associated with the defined primary outcomes and accounting for 20% attrition. In the absence of normative data, based on results of prior studies among emergency department enrolled PWUO that indicate modest uptake of MOUD (\sim 5% 191), and completing referrals to MOUD services (\sim 25% 192 194), we compute the power to detect significant effects.

Aim 2: Can the multimodal intervention be equitably implemented in clinical care?

Aim 2 is designed as a study of multi-perspective stakeholder feedback (N=50) of our proposed multimodal intervention to inform how best to integrate this approach into care teams using the RE-AIM framework to guide the evaluation of the intervention 177-179. Our sample size is driven by qualitative methods. We propose to recruit frontline providers (n=10), administrators (n=10), and a subset of PWUO participants randomized to intervention arm-1 (n=30) for a total N=50.

The RE-AIM and CFIR will be used as process and determinants frameworks that will allow us to adapt the intervention in arm 1 as it is unfolding, Additionally, they will be provided with snacks and coffee during their participation. and guide the evaluation of its effectiveness from the perspective of key stakeholder groups^{197–199}. Specifically, we will assess intervention **Reach** (among both PWUO and frontline providers); **E**ffectiveness (defined as PWUO linking with primary care-based buprenorphine treatment and social services, and as successful integration of PRCs in care teams); **A**doption (by providers and administrators); **I**mplementation (assessing fidelity of key implementation features and potential intervention adaptations during implementation, and resources and costs on a systems-level per administrator interviews and economic data analyzed in Aim 3); and **M**aintenance (assessing whether the intervention becomes integrated into routine practice, i.e., assessing the institutionalization of primary carebased buprenorphine treatment and social services (see *Table 3*).

We will complement RE-AIM with the CFIR to evaluate multi-level barriers/facilitators associated with intervention reach, effectiveness, adoption, implementation fidelity / adoption, and maintenance. The CFIR⁷⁶ specifies five main implementation determinants, including characteristics of the *Innovation* being implemented, the *Outer and Inner Settings* in which an intervention is being implemented, characteristics of *Individuals* involved with implementing, delivering, and/or receiving the innovation, and the implementation *Process*.

The RE-AIM and CFIR assessments will be based on the REDCap survey, EHR data (see *Table 2*), PRC communication logs and qualitative longitudinal interviews with PWUO, frontline providers (including PRCs), and administrators. These findings will capture data on the processes of intervention implementation as they occur, and the reasons why they unfolded in particular

Table 3. Implementation and cost-effectiveness measures within the RE-AIM framework

DIMENSIONS	MEASURES
Reach	Number, percentage, and representativeness of patients who participated in intervention
Effectiveness	Intervention impact on primary outcomes: percentage of patients linked to OBOT, non-study health service utilization (cost-offsets), health-related quality of life; and secondary outcomes: estimation of time to linkage, treatment days in OBOT, self-reported criminal justice involvement and activity (days incarcerated, criminal activity, arrests), social safety net services (unemployment income)
Adoption	Percentage / representativeness of providers / administrators engaged with intervention
Implementation	EHR data, survey data, micro-costing data on fixed and start-up cost associated with
	intervention, PRCs process notes, and downloaded text exchanges analyses to assess consistent delivery of intervention implementation
Maintenance	EHR data, survey data, micro-costing data on variable cost associated with intervention, PRCs process notes, and downloaded text exchanges analyses to preliminarily assess integration of the intervention into NYC Health+Hospitals system at end of data collection (time point 3).

ways at the individual, interpersonal (e.g., PRC-PWUO), and system-levels (see below for details on Interview Guide).

Approach

In-depth qualitative interviews will be conducted remotely using the HIPAA-compliant WebEx platform or in-person for PWUO participants with limited internet access. A key feature of the stakeholder groups is the between- and within-group heterogeneity (i.e., varying roles in intervention/responsibility/authority) that will enrich the interview data feedback on the relevance and utility of the intervention. These findings will enable us to evaluate the multimodal intervention from multiple perspectives and thus, better tailor it to the needs of all key stakeholders. There is also heterogeneity within each stakeholder group that can enrich the interviews. For instance, we will interview providers across the hierarchy from PRC to clinicians, and administrators, whereas in the PWUO sample, we anticipate some variety in treatment histories, structural barriers to care, technology savvy, and importantly, involvement, perceived benefit, and longitudinal engagement with the intervention.

Key CFIR topics incorporated in the PWUO interview guide to contextualize experiences with the intervention will include: 1) the intervention components, including ease or complexity to use, advantages and disadvantages relative to previously utilized OUD services, compatibility with participants' daily lives, barriers to sustained engagement, and participants' interpersonal interactions with the PRCs; 2) experiences with the inner settings of the social and clinical service organizations that participants were referred to and/or engaged with during the intervention, including stigma/discrimination, perceptions of the culture- and person-centeredness of the settings, and perceptions of the structural barriers and resources available to meet their needs (e.g., inclusive eligibility for services, timely appointments, care coordination/linkages, trauma-informed clinic/office design); 3) the outer settings in which participants live, including neighborhood safety and social barriers that influence OUD and that influence engagement with OUD services (e.g., OUD stigma in the community, telephone/internet access, peer support); 4) individual characteristics, including histories of opioid use and overdose, accessing OUD and social services; and 5) the **implementation process**, including interactions with the study team for recruitment and intervention delivery, as well as recommendations for improving intervention reach, effect, fidelity/adaptation, adoption and maintenance to overcome barriers that are identified throughout the interview. Frontline provider and administrator guides will cover: 1) the intervention components, including their ease or complexity to be integrated into routine care. their advantages and disadvantages relative to implementing other programs, intervention adaptability to local contexts, costs, and modifications made during the project. PRCs will also provide feedback on interactions with PWUO participants; 2) the inner settings of the participating institution, including PRC integration challenges into care teams (from both the PRC and other providers' perspectives), leadership support for the interventions, the degree of fit between the intervention and institutional missions/values, and institutional challenges providing primary care-based buprenorphine treatment (e.g., administrative, resource-related obstacles); 3) the outer settings of participating institutions, including potential barriers/facilitators to promote intervention reach in primary care, regulatory barriers/facilitators towards delivering OUD services; and perceptions on how CSDH impacts PWUO and their engagement with OUD and social services; 4) individual characteristics, including perceptions of, and experiences with, providing care for underserved Black / Latinx PWUO; and 5) the implementation process, including interactions with MPIs for intervention training, and feedback for improving intervention reach, effect, fidelity, adoption and maintenance.

Data Analysis

The analysis of the qualitative interviews will begin alongside the data collection. This will enable the timely identification of intervention implementation limitations and enable course correction as the study is unfolding. The interview transcripts will be content analyzed using a 7-step process

developed over the years by our team 120,122,148,204. This process allows for a systematic identification of subcode, codes and themes while keeping the data contextualized. Specifically, we will complete the following tasks: Step 1, identify the principal issues discussed by participants; Step 2, construct preliminary definitions of the analytic themes; Step 3, develop and apply core codes and subcodes to the initial set of interviews at each interview round. Blocks of text within text tagged with core codes will be assigned subcodes; Step 4, develop a provisional coding scheme; Step 5, test the provisional coding scheme by coding new transcripts; Step 6, reconcile coding differences and construct a final coding scheme; and Step 7, apply the coding scheme to the full dataset. Close reading of the coded interview transcripts will reveal data patterns withing each sample, but importantly, also highlight differences/similarities across the stakeholder groups that will inform intervention adaptation. For instance, an emerging qualitative data pattern midway through the data collection process (i.e., 6-month assessment) could be that PWUO are encountering regulation barriers and strongly recommend changes in guidelines that will afford them flexibility in enrollment and referrals to better engage PWUO in care. This lack of flexibility might also emerge in the administrators' interviews. This prismatic assessment of the intervention will enable us to draw inferences that will inform the refinement of the intervention as it unfolds. Qualitative findings from PWUO participants (N=30) will be analyzed in tandem with: a) the PRC notes on CSDH for these participants (i.e., the health habitus note); b) their electronic administrative data, EHR data (e.g., primary care missed visits); and c) their REDCap survey data (baseline, 3-,6, and 12-month follow up). For instance, we will analyze whether PWUO with numerous patient-initiated requests for telephone assistance from physicians (based on Participant Feedback Survey; a domain in the REDCap survey) who also report patientcenteredness will also be consistently engaged with the different features of the multimodal intervention. Such a triangulation of data conducted over time will inform intervention effectiveness and maintenance. Findings from the PRCs' interview data will be analyzed in tandem with: a) the downloaded PRC-PWUO participant text exchanges in intervention arm-1; b) the training and supervising notes of the MPIs as part of their PRC CSDH training and supervision; and c) notes from weekly research meetings pertaining to PRC experiences and their integration in care teams to add to the rigor of the intervention's assessment.

Intervention feasibility, fidelity and adaptation. Intervention feasibility will be assessed by examining fidelity to core components of the intervention (e.g., linkage to primary care-based buprenorphine treatment) and implementation strategies (e.g., training for PRCs in cultural and structural humility). Importantly, we will also examine any necessary intervention adaptations and the reasons for these changes, via the qualitative interview analysis. Again, we will employ different forms of data, including the PRC-PWUO participant text exchanges. Specifically, 10% of PRC-PWUO participant text exchanges will be reviewed among participants (n=25) providing written consent to this process to assess for consistency with CSDH-focused CSH training principles during the first two months following enrollment. Intervention fidelity will also rely on periodic reviews of the PRCs' notes to determine if they have elicited the cultural and social barriers and facilitating factors influencing PWUO engagement with services and how they are integrating these insights into their text exchanges with participants. Lastly, three cycles of indepth interviews with administrators, frontline providers including PRCs and PWUO participants in intervention arm 1 will assess intervention implementation as it unfolds in real time and inform modifications to the Al-driven texting algorithm and/or PRC training. The risk of contamination across intervention conditions is minimal given its technology mediated nature. However, to minimize this risk, study participants will be asked not to share any study content or experiences with peers. Potential contamination will also be assessed by asking participants if they heard about the study or knew any participants prior to entry.

Aim 3: How Cost-Effective is the multimodal intervention?

Aim 3 is an economic evaluation of the proposed multimodal intervention using well-established quidelines of prospective economic evaluations alongside clinical trials. 102,194,195 Outcome measures will be analyzed using multivariable generalized-linear mixed models (GLMMs) to adjust for potential confounding factors and the skewed distributions commonly associated with healthcare cost data and censored outcomes (e.g., QALY). 195 The GLMM, an extension of the GLM, allows the most appropriate mean and variance functions to be chosen based on the observed data, 195 as well as for the inclusion of random effects. 202 The primary outcomes for Aim 3a will be the budget impact tool consolidating the resources and associated costs required to implement and sustain the PRC-participant text contact + interactive text messaging, and interactive text messaging only interventions compared to TAU. The primary outcome of Aim 3b will be the incremental cost-effectiveness ratio (ICER), 194,195 defined here as the incremental mean cost between the two intervention arms and TAU divided by the incremental mean effectiveness (QALY and OUD treatment days) of the two arms calculated separately. HRQoL is increasingly recognized as a key indicator of patient well-being that is not captured in clinical measures. The QALY is a measure that combines the HRQoL associated with an individual's health state and their time spent in that state. 102,194,195 The QALY is recommended as the primary effectiveness measure in economic evaluations due to its ability to be compared across interventions and disorders, and its association with commonly-accepted value thresholds (i.e., cost-per-QALY). 194,195 OUD treatment days is an important continuous measure of effectiveness for clinical stakeholders and calculating cost-per-OUD treatment days enables comparisons with prior published economic evaluations of OUD interventions reporting similar clinical effectiveness measures. 112 As part of the process of estimating ICERS, we will be able to test the 6- and 12-month post-intervention differences between arms of a) the average total costs to the healthcare sector, state policymaker, and society by resource categories; and b) the average QALYs and OUD treatment days; thus, two ICERs will be calculated for each of the three stakeholder perspectives for each of the aforementioned evaluation periods.

Health Economic Measures

Health-Related Quality of Life (HRQoL) will be measured using the validated Patient-Reported Outcomes Measurement Information System (PROMIS)—Preference (PROPr) instrument. PROMIS (including PROPr) was developed using item response theory (IRT), with support from the NIH. Because of its IRT foundation, PROPr is more flexible, and improves upon common deficiencies of alternative HRQoL instruments. The PROPr scoring system uses the respondent's scores for each of the following domains to calculate a HRQoL index value that represents the general US population's preference for a respondent's health state: Cognitive Function—Abilities, Depression, Anxiety Fatigue, Pain Interference, Pain Intensity, Physical Function, Sleep Disturbance, and Ability to Participate in Social Roles and Activities. HRQoL values produced by PROPr range from -0.022 to 1, where 0 represents death, 1 represents perfect health, and values below 0 represent states perceived to be worse than death. The HRQoL value is then used to calculate regression-adjusted QALYs per study arm as our team and others have done in similar studies. 103,122–125,238

Healthcare, Non-Medical and Other Services. The utilization of healthcare services by participants will be measured using study data and the Timeline Follow-Back (TLFB)¹⁹¹ methodology via the Non-study Medical and Other Services (NSMOS) form. Healthcare services will include inpatient, outpatient, telehealth, and ED services; opioid use disorder treatment

medications, and residential and outpatient substance use disorder treatment days; hospital detoxification days; and mental health treatment visits. The reliability and validity of self-reported data is well established over recall periods similar to those in this proposal 196,204,239–241. Non-medical and other resources required to determine the costs from the state policymaker and societal perspectives (e.g., recidivism, workplace productivity, etc.) will be collected via the NSMOS form, Addiction Severity Index – *Lite* (ASI), and other study instruments. The NSMOS, ASI, and other study instruments have been successfully used by the economic team in prior economic evaluation studies 122,124,125, and is currently in-use in numerous clinical trials of substance use disorder treatments, including those associated with the NIDA Clinical Trials Network (CTN) and Justice Community Opioid Innovation Network (JCOIN) 120,123,242.

Aim 3 Data Analysis

Aim 3a will involve the development of a customized budget impact tool using implementation-related data collected by the trial to capture all relevant healthcare resources (see "Intervention Costs") following recommended methods.²⁰⁰ The resource-costing method will be used to value all relevant, non-research resources. Resource costing involves determining a per-unit price-weight for each relevant resource and multiplying the price-weights by the number of resource units utilized. The budget impact tool will include 5 Microsoft Excel worksheets, with drop-down menus incorporated throughout to increase ease of use, and limit data-entry errors. The first worksheet is a dashboard that is automated by linking data from the other worksheets and displays the total costs differentiated by resource category identified in the microcosting analysis (see Intervention Costs). The remaining worksheets include the various resources that could be associated with different OUD treatment models, and their associated unit costs. Thus, users will select the quantity of each relevant resource, change the unit costs if desired and be able to view detailed cost estimates by fixed, variable, and time-dependent components.

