The sample size, N=252, was chosen to provide sufficient power for analyses associated with the defined primary outcomes and accounting for 20% attrition. In the absence of normative data, based on results of prior studies among emergency department enrolled PWUO that indicate modest uptake of MOUD (~5%¹⁹¹), and completing referrals to MOUD services (~25%¹⁹²⁻¹⁹⁴), we compute the power to detect significant effects. Using these estimates as the baseline, we anticipate that interactive texting will increase completing referrals to primary care from 25% to 35% ¹⁹⁵⁻¹⁹⁷. The combination of interactive texting and PRC support will enhance time to completing referrals to primary care from 25% to 45%. These anticipated changes indicate odds ratios for intervention versus TAU (effect size) of between 1.5 to 2.0 for OUD-related outcomes. We use these estimated odds ratios (ORs) as the proxy for the rate in treatment versus the control. Evidence from methodological studies assert a useful equivalence involving the hazard ratio (HR), such that when the PH assumption is reasonable, the HR is equivalent to the odds that a randomly chosen person with hazard represented in the numerator will experience the event of interest before a randomly chosen person with hazard represented in the denominator 198-200. The power to detect these effects with α =0.05 (two-tailed) using log-rank comparisons for survival outcomes via the power procedure in SAS v9.4 is ~80%.

Enrollment, Consent and Workflow

Over a 2-year period, Black / Latinx PWUO (N=252) identified in the ED or community by the study team using the electronic medical records (EMR) or self-report will be screened and enrolled by the study team. Specifically, ED-recruited Black and Latinx PWUOs with a positive urine toxicology per the Hospital EMR or self-reporting illicit opioid use among PWUO approached in community settings and confirmed with random saliva toxicology testing will be enrolled over a 2-year period. Community-recruited PWUO participants will complete enrollment in the in private conference rooms located in Lincoln Hospital or START Treatment and Recovery centers or in the NYS OMH Harlem field office site. Given the ethical importance to expand enrollment of vulnerable and hard-to-reach persons living with substance use, including women, unstably housed, and uninsured adults, we will provide reimbursement for peer-driven recruitment (\$25, max 3 referrals per participant).

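### The three-arm primary analysis names no primary contrast and no multiplicity control, so two-sided family-wise error could reach about 9% to 12% against a stated 5%

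*Combined protocol and SAP*

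**What the plan says.** Under Proposed Analyses, the Aim 1 text begins "Our primary hypothesis is that the rate of linkage to OBOT" and ranks the arms: texting plus PRC (arm-1), then texting only (arm-2), then TAU. The analysis is a Cox proportional hazards model for time to linkage with assigned group as the only explanatory variable. Data Entry & Analysis repeats the approach as a question of whether the groups differ.

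Alpha appears once, in the Cohort section on sample size: "α =0.05 (two-tailed) using log-rank comparisons for survival outcomes", with power given as "via the power procedure in SAS v9.4 is ~80" per cent. The effects there are stated for both active arms against control: "odds ratios for intervention versus TAU (effect size) of between 1.5 to 2.0 for OUD-related outcomes". The underlying rates are "interactive texting will increase completing referrals to primary care from 25% to 35" per cent for arm-2, and for arm-1 the combination "will enhance time to completing referrals to primary care from 25% to 45" per cent.

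Neither section says which contrast decides success, whether a global or trend test comes first, in what order contrasts are tested, or how alpha is shared.

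**The concern.** An ordering of three arms involves up to three pairwise comparisons, and the Aim 1 statement in the Study Synopsis sets all three arms against each other. With one alpha and no rule, each hazard ratio from the Cox model can be read at 0.05 and any significant one presented as support for the primary hypothesis. The error rate of the primary claim would then exceed the stated 5%.

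The choice of what counts as success could also be made after the data are seen. A mixed result (arm-1 better than TAU, arm-2 not) is quite likely at the assumed rates, and the plan does not say whether it would support the hypothesis.

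**Working it through.** **Inputs.** 252 participants randomized 1:1:1, so 84 per arm; linkage 25% (TAU), 35% (arm-2), 45% (arm-1); two-sided alpha 0.05, critical value 1.96. The rates and alpha are from Cohort; the allocation and arm sizes are from Study Design and Study Procedures.

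**Which contrast the stated power describes.** Under proportional hazards, HR = ln(1 − p1)/ln(1 − p0), expected events d = 84 × (p0 + p1), and power ≈ Φ(√(d/4) × ln HR − 1.96).

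| Contrast | HR | Events | Power |
|---|---|---|---|
| arm-1 vs TAU | ln 0.55/ln 0.75 = 2.08 | 84 × 0.70 = 58.8 | 80% |
| arm-2 vs TAU | ln 0.65/ln 0.75 = 1.50 | 84 × 0.60 = 50.4 | 30% |
| arm-1 vs arm-2 | ln 0.55/ln 0.65 = 1.39 | 84 × 0.80 = 67.2 | 27% |

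The stated figure of about 80% matches one unadjusted pairwise test, arm-1 vs TAU, with no attrition. A 2-df test across the three arms at these hazard ratios has about 68%. With 20% attrition (67.2 per arm), arm-1 vs TAU has 71%; that is a separate matter.

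**Family-wise error under the complete null.** With equal arms, two contrasts that share an arm have correlation 0.5 in absolute value.

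- All three pairs, two-sided: P(studentized range for 3 groups > 1.96 × √2 = 2.77) = 12.2%.
- Two contrasts with TAU, two-sided: 1 − P(|Z1| ≤ 1.96 and |Z2| ≤ 1.96, correlation 0.5) = 9.1%.
- Hypothesised direction only: 6.6% for three contrasts and 4.5% for two (4 million simulated null trials), against 2.5% for a single two-sided 0.05 test.

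The relative inflation is similar on either scale: 12.2/5 = 2.4 and 9.1/5 = 1.8 two-sided; 6.6/2.5 = 2.6 and 4.5/2.5 = 1.8 in the hypothesised direction. A simulation of log-rank tests at 84 per arm, 25% linkage throughout and no dropout (20,000 trials) gave 12.0%, 9.0%, 6.5% and 4.4%, so the normal approximation is adequate here.

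**Readings that would control the error.**

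- A 2-df test as a gate, then pairwise tests at 0.05: 5.0% under the complete null.
- Success only if both adjacent steps (arm-1 over arm-2, and arm-2 over TAU) are significant: far below 5%, but simulated power at 25/35/45% is only about 2.6%, because both steps are weak and share arm-2 in opposite directions.

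**Arm-1 vs TAU as the gate.** Take every pattern of true null hypotheses:

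- If arm-1 and TAU are equal, a false claim on any contrast first requires the gate to be passed, which has probability 5%.
- If arm-1 and TAU differ, arm-2 cannot equal both, so at most one of the two remaining null hypotheses is true, and it is tested at 5%.

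Family-wise error is therefore at most 5% in every case. Simulated power at 25/35/45%, 84 per arm, no dropout:

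| Contrast | Each alone at 0.05 | With the gate |
|---|---|---|
| arm-1 vs TAU | about 79% | about 79% |
| arm-2 vs TAU | about 29% | about 28% |
| arm-1 vs arm-2 | about 27% | about 25% |

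**The case against.** The plan never says that unadjusted pairwise contrasts will be used. Its Cox wording fits a 2-df group test, and a 2-df gate before pairwise tests controls the error in a three-arm trial. The sample-size text frames effects against TAU only, which points to two contrasts and 9%, not 12%. If success means demonstrating the whole ordering, there is no inflation at all.

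Much of this stands. A reader might infer that the plan commits to three unadjusted tests; the documents do not support that, because they name no contrasts. A reader might also infer a 12% chance of a false efficacy claim. That is wrong too: 12% counts significant results in either direction, including TAU beating texting, and false wins in the hypothesised direction occur in 4.5% to 6.6% of null trials.

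The objection does not close the gap. No 2-df gate is stated, and a group test alone cannot show which arm is better than which. The whole-ordering rule is not stated either, and its power of about 2.6% cannot be squared with a stated power of about 80%. The power text refers to log-rank comparisons in the plural at 0.05 and matches an unadjusted pairwise test.

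**Conclusion.** The point holds as an omission and should be fixed before analysis. The plan does not define the primary contrasts or control multiplicity. Depending on an unstated choice, two-sided family-wise error under the complete null is at or below 5% (a 2-df gate or a whole-ordering rule), about 9% (two contrasts with TAU) or about 12% (all three).

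These figures assume equal allocation, all three arms truly alike, and each contrast read at two-sided 0.05. The power figures assume the plan's rates of 25/35/45%, proportional hazards, 84 per arm and no dropout; all would be lower with the attrition that the plan expects.

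**What to change.** Add to the Aim 1 analysis: arm-1 vs TAU is the primary contrast, tested first at two-sided 0.05. Only if it is significant are arm-2 vs TAU and arm-1 vs arm-2 tested, each at two-sided 0.05. Report all three hazard ratios with confidence intervals whatever the outcome, and state that the sample-size power refers to the first contrast.

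The cost is SAP wording and the small power losses tabulated above. One consequence should be accepted openly: if arm-1 vs TAU is not significant, no confirmatory claim can be made for texting only.

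A strict three-step sequence (arm-1 vs TAU, then arm-2 vs TAU, then arm-1 vs arm-2) should not be used. It would cut power for arm-1 vs arm-2 from about 27% to about 2.6% and so nearly remove the test of what peer coaching adds. Dunnett or Tukey adjustment also controls the error, but at HR 2.0 and 84 per arm it lowers arm-1 vs TAU power from 76% to 67% or 62%.
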